## 9. STATISTICAL CONSIDERATIONS

### 9.1 General Design Issues

This shall be a double-blinded randomized, placebo-controlled, exploratory phase I-IIa proof of concept clinical trial. It shall include adults aged 18-80 years with untreated CA of any genotype, who suffered a symptomatic lesional hemorrhage within the preceding year. We plan to enroll 80 subjects during years 1-3, specifically targeting cases whose hemorrhagic lesion was not resected, with greatest risk of rebleeding in subsequent 2 years. Inclusion and exclusion criteria aim to exclude cases receiving prior statin therapy in any form or for any indication in the past year, cases at high risk for statin intolerance, and other customary exclusions in similar trials. Children will not be enrolled, per IND Exemption restriction for this trial.

Enrolled subjects will be blinded to treatment rendered, as will the investigators conducting and reporting biomarker studies (including QSM, the primary outcome measure),

and PIs, the clinical personnel caring for the patient, and DCC staff. The safety monitoring team will have access to A/B treatment designations but will be blinded to which group A and B are assigned, unless a concern is raised and consideration to suspend enrollment in the trial. Atorvastatin and placebo capsules will be formulated by a third party pharmacy in two color coded tiers (green and blue) representing different doses of atorvastatin (40 and 80 mg) or placebo. The 40 mg dose (or color matched placebo capsule) will be used in subjects who develop mild side effects on the initial dose target of 80 mg/day.

After satisfying the screening criteria, patients will be assigned a subject number and randomized to the atorvastatin or placebo arm in a 1:1 ratio (See section 3.3 Randomization). This will be implemented upon subject enrollment, and communicated to the Research Pharmacy at the Chicago site via the web-based Electronic Data Capture (EDC) system. Administration of study drug shall continue thereafter, at once daily oral dose for 24 months, with **scheduled visits and repeat imaging at 12 and 24 months from enrollment, and follow-up calls quarterly, and weekly feed back on compliance by electronic monitoring device**. Safety endpoints include a symptomatic intracranial hemorrhage, from the index CA lesion or another source, or a serious adverse event (SAE) necessitating drug discontinuation (Protocol Section 8). If new symptoms arise at any point after starting the study or relevant laboratory test abnormalities, subjects will be contacted by the TN for further assessment and instructions regarding continuation of study intervention, dose de-escalation or discontinuation, based on the study **adverse events management protocol** (See Protocol Section 7). This approach is similar to that used in other statin trials (84, 85, 99, 100, 102, 106, 107, 109).

## 9.2 Outcomes

The primary outcome is the mean percent change in lesional QSM per year (called the change score). Each patient contributes two outcome measurements (at year 1 and year 2) based on intention-to-treat. Evaluation of the intervention on this outcome will be performed as a time-averaged difference between two arms using a repeated measures analysis implemented as a linear mixed model, adjusted for gender (110). Patients with outcome measurements in both periods will be included in the initial intention-to-treat analysis. In cases with multiple lesions, only QSM measurements in the lesion with initial hemorrhage (index lesion) shall be considered for the primary outcome assessment. A secondary analysis of the percent QSM change per year shall be conducted per treatment rendered for all patients with at least one annual epoch of measurements.

Secondary outcomes shall include:

- Changes in DCEQP vascular permeability measurements in the index lesion and in brain (white matter far from lesion),
- Rates of QSM and DCEQP biomarker events, representing increases in index lesional QSM or DCEQP above previously articulated “biomarker thresholds” (58); rates of clinically overt hemorrhages in the index lesion per

adjudicated criteria; and rates of lesional expansion, defined as an increase in maximum lesion diameter on T2-weighted sequences by 2 mm or more.

- Adverse event rates and serious adverse event rates, and drug compliance
- Changes in functional outcome (mRS, MMSE, Euro-QoL 5D, Euro-QoL VAS, Neuro-QoL evaluations)
- ROCK Activity Assay on Peripheral leukocytes (pMBS/GADPH ratio in immunoblots for each subject/visit)
- Impact of sex, genotype and lesion location on primary and secondary outcomes (pre specified subgroup analyses)

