## 1. STUDY OBJECTIVES

The **Primary Aim** of the study is to assess whether the proposed intervention produces evidence of QSM biomarker activity (indicative of reduced or increased lesional bleeding) during 2 years of prospective follow-up after a recent symptomatic hemorrhage. **The primary outcome is the mean percent change in QSM (called the change score) per year.** Reduced CA hemorrhage would be a signal proof of concept of potential benefit, and increased hemorrhage a potential signal of risk. Primary analysis shall be based on intention to treat, and secondary analysis shall examine treatment rendered, considering attrition and compliance. In cases with multiple lesions, QSM measurements in the lesion with initial SH (index lesion) shall be considered for the primary outcome assessment.

**Secondary Aims** shall assess (1) a second biomarker (DCEQP permeability in lesion and brain), (2) ROCK activity on peripheral blood leukocytes and on any excised lesion specimens during the course of the study, (3) clinical event rates, (4) adverse events, and (5) functional outcomes in placebo versus treatment; and (6) we shall query pre-specified subgroups.

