We recently reported the first prospective assessment of QSM during longitudinal follow-up of human CCM subjects, and correlated paired QSM assessments during 1-year epochs with new clinical events (58). Among cases without recent bleeding or lesion growth within a year of the first measurement, CCM lesions that remained stable during longitudinal follow-up had a tiny average decrease (-3.2%) in mean lesional QSM. CCMs with demonstrated growth or symptomatic bleeding exhibited a significant increase (+44%) in mean lesional QSM (Figure 6). Receiver operating curves (ROC) of QSM change in individual subjects demonstrated a sensitivity of 82.29% and specificity of 88.89% at a +5.81% threshold change, highly significant ( $p = 0.0004$ ), with a mere **+5.81% QSM change. These results link a robust QSM change directly to clinical events, and define a threshold QSM change as a sensitive and specific biomarker event.**

**QSM change and clinical events in CAs after recent Symptomatic Hemorrhage.** In further pilot studies, we assessed lesional QSM change during prospective **follow-up of a pilot cohort of CA patients with a clinical bleed within the prior year (meeting the proposed trial criteria)** (59).

Sixteen subjects followed for 1 or 2 years (total 22 person-year epochs), underwent paired QSM assessments at the beginning and end of each person-year epoch. Mean QSM in the index CA hemorrhagic lesion increased by an average of +7.93% per person-

[figure not shown]

year epoch in the full cohort. Closer examination revealed 10/22 epochs with a documented threshold biomarker event ( $\geq 6\%$  QSM increase). This was twice as frequent as clinical events. No clinical event occurred without a threshold increase in QSM (Figure 7). A primary aim of the proposed trial shall explore whether the change in QSM is altered by statin treatment. A secondary aim shall explore the relationship of QSM change to clinical events in statin and placebo treated subjects.

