### **9.3.2 Potential Missing Data, Attrition and Premature Trial Endpoint**

We considered all potential causes of missing data and we developed strategies to minimize and mitigate them. In initial pilot studies, 34 of 177 (19%) QSM assessments in CA patients were unusable due to technical reasons (mostly patient movement during image acquisition). We eliminated this problem in the most recent 25 consecutive cases with specific patient instructions. We now implement a further step of reviewing the QSM acquisition, and rapidly processing it (10 minutes on local Matlab computer terminals in our laboratory). This allows us to repeat the QSM acquisition if needed, before proceeding with contrast injection for DCEQP measurements. This “chaperoned biomarker acquisition” reduces to virtually zero the rate of missing QSM measures (See letter by [name] and Protocol Section 6.5). We nevertheless project up to 10% missing biomarker data related to imaging (claustrophobia, etc.). We further project an additional 10% missing data due to imperfect follow-up, higher than that recorded in recent trials conducted by our teams (113, 114).

Up to 20% of subjects randomized to atorvastatin (10% of trial subjects) might not tolerate the 80 mg/day dose. Many will continue the drug at the lower dose. In fact, **serious side effects or intolerance of the lower dose are expected to result in attrition in less than 5% of cases**, per extensive meta-analyses of trial experience with the study drug (See Protection of Human Subjects; and Protocol section 7.3). Another **20-30% of cases might reach a prespecified study endpoint** because of SH, and they would also stop the drug before the end of the 2-years follow-up. All subjects who stop the drug, and those with non-compliance as defined, will still be followed for the full 2 years with scheduled clinical and imaging assessments, and will be included in the **primary analysis per intention-to-treat**.

To permit secondary analysis per treatment rendered, at the power and Type I error described above, we decided to **expand the sample size by an ample 37.5%, factoring the highest combined estimates of missing data and attrition.**

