### **9.5 Data analysis**

Exploratory analyses for quality assurance and understanding of missing data patterns and distributions will be performed on the outcomes and all measurements to be used in the primary and secondary analyses. For the **primary aim**, a linear mixed model will be used that adjusts for gender to evaluate the difference between the two arms in the QSM change of the index hemorrhagic lesion per patient. Adjustment for gender is necessary because the patients will be randomized by gender stratification. Not control-

ling for stratification variables can lead to upwardly biased standard errors and a decreased power (116). The model accounts for within-patient correlation between the measurements (117, 118). Patients with outcome measurements in both periods will be included in the initial intention-to-treat analysis. A secondary analysis of the percent QSM change per year shall be conducted per treatment rendered for all patients with at least one annual epoch of measurements. Significance levels are assumed as per sample size calculations.

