To address **secondary aims**, each of the other outcomes will be analyzed with a similar approach, first per intention-to-treat sample in patients receiving two annual epochs of follow-up, and second by treatment-rendered in all patients with at least one annual epoch of measurements. To assess the difference in level of DCEQP permeability in lesion and brain between the two arms, a linear mixed model adjusted for gender as described for QSM will be used to evaluate the difference in percent change per year in lesional and WMF permeability. A similar adjusted linear logistic mixed model for the binary outcomes will be used to evaluate the difference between the two arms in the rates of symptomatic hemorrhage (per adjudicated definition), lesion expansion, and “biomarker event” (increase in QSM during an epoch above the pre-defined 6% threshold). To assess the difference of event rates for adverse events (AEs) per patient, an adjusted Poisson linear mixed model controlling for gender will be used to regress count outcomes in order to evaluate the difference in AE event rates between the two treatment arms. The AEs will be assigned preferred terms per body systems according to the Medical Dictionary for Drug Regulatory Affairs (MEDDRA) classification of the WHO terminology. AEs (categorized by body system) and abnormal laboratory data will be summarized and compared by treatment group. The compliance rate, general attrition rate and the attrition rate due to adverse events between the two groups shall also be compared. For analysis of leukocyte ROCK activity and functional outcomes (mRS, Euro QOL 5D and VAS, Neuro QOL Communication, and mini-MS score), an adjusted linear mixed model will be used to evaluate the difference in respective outcome score change per year between the two arms. We will report point-estimates, confidence intervals, and p-values for each analysis.

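### The primary QSM analysis is called intention-to-treat but admits only patients with both annual change scores, and read literally the same rule reaches the first modelled hemorrhage and adverse-event comparisons

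*Combined protocol and SAP*

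**What the plan says.** Section 1 states the principle: "Primary analysis shall be based on intention to treat, and secondary analysis shall examine treatment rendered, considering attrition and compliance". Sections 9.2 and 9.5 then define the set: "Patients with outcome measurements in both periods will be included in the initial intention-to-treat analysis". The analysis described next in both sections "shall be conducted per treatment rendered for all patients with at least one annual epoch of measurements". The contrast shows that the both-periods wording is a restriction and not a loose way of saying everyone.

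For the other outcomes, 9.5 plans the analysis "first per intention-to-treat sample in patients receiving two annual epochs of follow-up", and the models that follow include symptomatic hemorrhage and adverse-event counts.

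Section 9.3.2 says: "All subjects who stop the drug, and those with non-compliance as defined, will still be followed for the full 2 years". The same sentence places these patients in the "primary analysis per intention-to-treat". That section allows for up to 10% missing imaging data and then adds: "We further project an additional 10% missing data due to imperfect follow-up".

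Two other parts of 9.5 matter. The compliance subsection sets a 90% threshold for treatment-rendered analyses. The missing-data subsection plans multiple imputation under missing-at-random and a tipping-point approach, both as sensitivity analyses.

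**The concern.** Requiring both scores selects patients on something observed after randomization. No section defines a primary set of all randomized patients with the data they have. A patient with one valid annual score is absent from the primary result, and can enter only an analysis conditioned on compliance or a sensitivity imputation. This departs from the principle in section 1. It also departs from 9.3.2 for any drug stopper or non-complier who misses a score, so two analysts could build different primary datasets.

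Missing scores may be related to outcome. Section 9.3.2 expects 20-30% of cases to reach a hemorrhage endpoint, section 7.3.1 has the bled lesion considered for treatment, and section 8 lists resection among the discontinuation events. That an excised index lesion yields no later QSM score is an inference.

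For safety, a literal reading of 9.5 leaves a patient who dies or withdraws before month 24 out of the first modelled hemorrhage and adverse-event comparison. One lost before month 12 is left out of the second as well.

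**Working it through.** **The plan's own figure.** Inputs from 9.3.1: difference 20 points, SD 30, two scores per patient, within-person correlation rho = 0, two-sided alpha 0.05, power 0.9. The variance of a patient's mean score is 900(1 + rho)/2 = 450. The normal approximation gives n = 2 × (1.960 + 1.282)² × 450/400 = 23.6, or 24 per arm. The noncentral t gives 25, and 44 and 17 for 15 and 25 points, exactly as stated. Enrolment is 25/(1 − 0.375) = 40 per arm. The worst-case completers set is therefore the 25 per arm on which power rests.

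**Precision.** Let Nc be completers and Ns year-1-only patients per arm. Pooling all scores with a common effect, information per arm is 2Nc/[900(1 + rho)] + Ns/900, SE = √(2/information), and power = Φ(difference/SE − 1.96). Weighting the years equally at rho = 0, SE = ½√[1800/(Nc + Ns) + 1800/Nc].

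Worst case (Nc = 25, rho = 0):

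| Analysis | SE | Power, 20 points | Power, 15 points |
|---|---|---|---|
| Completers (Ns = 0) | 6.00 | 91.5% | 70.5% |
| All epochs, pooled (Ns = 15) | √(1800/65) = 5.26 | 96.7% | 81.3% |
| All epochs, years equally weighted (Ns = 15) | ½√(45 + 72) = 5.41 | 95.9% | 79.2% |

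The last two rows assume that all 15 have a year-1 score. At the pilot correlation of −0.6 the pooled SE goes only from 3.79 to 3.59.

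Projected 10% + 10% loss, taken as 8 of 40 per arm without both scores (Nc = 32): the completers' SE is √(1800/64) = 5.30. If all 8 have year 1, it is 5.00 pooled or 5.03 equally weighted. If 4 do, it is about 5.15 either way. If none do, it stays at 5.30.

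**Weighting.** With 40 year-1 and 25 year-2 scores per arm, pooling gives year 1 a weight of 40/65 = 62%. If the effect differs by year, the planned time-averaged contrast shifts; equal weighting prevents this.

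**Bias in QSM (illustrative).** From section 2.2: +44% in epochs with bleeding or growth and −3.2% in stable ones, both from previously stable lesions, and +7.93% overall in the recent-hemorrhage pilot. Combining them assumes that the two cohorts are comparable. The share of bleeding-type epochs is p = (7.93 + 3.2)/47.2 = 0.236. Suppose the drug halves or doubles p, the years are independent, and a fraction q of bleeders give no later QSM. The documents do not give q. The only anchor is 7 of 37 patients excised (0.19, section 3.1), who were seen before enrolment.

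Among patients retained, p becomes f(p) = p(1 − q)/(1 − pq). If loss follows the month-12 scan, only the completers' year-1 difference is distorted, and it is averaged with an intact year-2 difference. If excision precedes the next scan, both years are distorted, and completers and all-epoch analyses agree.

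| Scenario | True | Lost after month-12 scan: completers | Same: all epochs | Excised before next scan: both analyses |
|---|---|---|---|---|
| p halved, q = 0.19 | 5.56 | 5.20 | 5.56 | 4.83 |
| p halved, q = 0.5 | 5.56 | 4.46 | 5.56 | 3.35 |
| p doubled, q = 0.19 | −11.13 | −10.75 | −11.13 | −10.37 |
| p doubled, q = 0.5 | −11.13 | −9.69 | −11.13 | −8.26 |

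At q = 0.19 the bias is about 0.4 points in the first situation and 0.7 to 0.8 in the second.

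**Hemorrhage (illustrative).** For two-year risk R, the annual risk is a = 1 − √(1 − R). If a fraction q of year-1 bleeders is lost, completers show [a(1 − q) + (1 − a)a]/(1 − aq). With q = 0.1 (assumed), R = 32% (section 9.4.2 gives 32.1%) appears as 30.8%, and R = 50% (assumed) as 48.5%. The difference moves from 18.0 to 17.7 points.

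**The case against.** The strongest reply is that the text is narrower and better protected than it looks. Much of that stands.

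- **Section 9.3.2.** A reader might infer that it flatly contradicts 9.2. It does not: it concerns people who stop drug, whereas 9.2 concerns missing scores. A drug stopper with both scores is in under either section.
- **Section 9.3.3.** Mixing one-year and two-year patients is unavoidable at an interim look and is not itself a defect.
- **Discarded data.** A reader might infer that year-1 data are thrown away. They are absent from the primary analysis only, and can enter the treatment-rendered and imputation analyses.
- **Safety.** A reader might infer that deaths and bleeds vanish from the safety assessment. The documents do not support that. The adverse-event summaries and attrition comparisons in 9.5 do not repeat the limit, section 9.4.2 monitors hemorrhage continuously, section 10.4.2.3 records events from randomization to the end of follow-up, and section 8 keeps patients at a safety endpoint in follow-up to month 24. Only the modelled comparisons are affected, and only on a literal reading.
- **Baseline and month-24 scans only.** That such a patient has no annual score rests on the pilot description, where subjects "underwent paired QSM assessments at the beginning and end of each person-year epoch". No trial section excludes the patient outright, but none says how to handle the case.
- **The anchor.** The 7 of 37 preceded enrolment, while trial patients are those in whom surgery was considered and not done. It says little directly about excision after an on-trial rebleed. Independent years also sit uneasily with the pilot correlation.

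The reply does not remove the core. A mixed model copes with incomplete patients only if they enter it, and sensitivity imputation does not repair the definition of the primary set.

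**Conclusion.** The point holds as a defect in the definition of the analysis sets that should be fixed; it is not a fatal flaw. The primary set is completers by construction and conflicts with section 1, and with 9.3.2 in the narrow case of drug stoppers or non-compliers who miss a score.

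A reader might infer that the trial is underpowered or the result badly biased. Under the plan's own assumptions, power is intact. The precision forgone is moderate at the 37.5% worst case and small at the projected loss, and there is nothing to gain if the excluded patients have no year-1 score. The bias figures rest on an undocumented q and a simple model. At the one indirect anchor they are below one point, and only the part arising after an obtained month-12 scan is recoverable. The hemorrhage distortion is 0.3 points in the illustration and depends on reading 9.5 literally.

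**What to change.** Amend 9.2 and 9.5 before unblinding:

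1. Fit the primary mixed model to every randomized patient with one or more annual QSM change scores, by randomized arm, using all available epochs. Include epoch and treatment-by-epoch terms, and take the equally weighted average of the year-1 and year-2 differences as the estimate. This preserves the planned time-averaged contrast.
2. Analyse adverse-event and serious adverse-event counts in all randomized patients, with log follow-up time as an offset in the Poisson model. Analyse hemorrhage in all randomized patients by a time-at-risk method (time to first event, or complementary log-log with an offset), since a follow-up offset does not fit the planned logistic model.
3. Make the both-epochs analysis a sensitivity analysis. Keep the imputation and tipping-point analyses for patients whose scan after a bleed is missing, and state that they also cover patients with only baseline and month-24 scans.
4. Align 9.3.2 with the same set.

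No new patients, visits or scans are needed. The costs are reliance on missing-at-random for single-epoch patients and a small change of model for hemorrhage. The change does not remove bias when the lesion is excised before the next scan, which is why the tipping-point analysis must stay.

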## 9.3 Sample Size and Accrual

### 9.3.1 Sample size and Treatment Effect Estimation

Sample size calculations were based on providing sufficient power to test the primary hypothesis, that the proposed intervention impacts QSM biomarker activity (indicative of reduced or increased lesional bleeding) during 2 years of prospective follow-up after a recent CA SH. **The primary outcome is the mean % change in lesional QSM per year (called the change score).** Each patient contributes two outcome measurements (at year 1 and year 2, i.e. epochs). Evaluation of the intervention on this outcome will be performed as a time-averaged difference between two arms using a repeated measures analysis implemented as a linear mixed model and intention-to-treat principle (110).

**Estimating a “First-in-Man” treatment effect on a biomarker** can be difficult when such effect is demonstrated mechanistically but the translation to a human effect size remains unknown (111). Based on pilot data linking QSM change to clinical events, **we propose a minimum, clinically meaningful and mechanistically plausible treatment effect to be a 20% absolute difference in the mean change score.** It would be “a minimum expected effect”, <1/2 the mean 44% QSM increase observed with CA bleed or growth during longitudinal 1-year follow-up of previously stable lesions; and “clinically meaningful”, > 3X the threshold of QSM change associated with maximum sensitivity-specificity on ROC analyses (58). The absolute QSM effect size postulated herein is “plausible mechanistically”. It would be 0.0068 ppm [20% of 0.0340 ppm mean QSM change observed during follow-up of CA with SH (59)], 6-22 folds lower than the observed range of atorvastatin treatment effect on Perls stain intensity in *Ccm1* and *Ccm3* murine models (Figures 2, 3, 5).

One-year %QSM change in 16 pilot study patients (Figure 7), followed for either 1 or 2 years (22 patient-year epochs), was used to estimate the 1-year/patient standard deviation and within-patient correlation of the primary outcome in trial candidates. A sample size calculation was performed using a repeated measures analysis of two annual percent QSM change scores, assuming a two-tailed test, power = 0.9 and alpha = 0.05 (112). The actual within person correction from the pilot data was estimated at approximately -0.6 (Spearman); however, as this was based on only 6 patients with two-year’s

worth of data, we chose the more conservative within person correlation of 0 for our sample size estimates. In addition, we assumed a common standard deviation of 30 for the mean percent change score, which to be conservative is about 20% larger than the standard deviation in our pilot data. **To detect a 20% absolute difference between the mean change score in each arm, based on two annual change scores measured per patient (at years 1 and 2), 25 patients per arm would be required.** To detect a smaller or larger effect size, an absolute difference of 15% or 25%, 44 or 17 patients per arm would be required, respectively (Hintze 2014, PASS v13, NCSS, Kaysville, Utah, USA [www.ncss.com](http://www.ncss.com)). The sample size was further expanded by 37.5% to accommodate the highest estimate of missing data from all causes as discussed below. Hence we shall aim to enroll **40 patients/arm, 80 total subjects.**

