#### Quantitative Susceptibility Mapping (QSM) as a Biomarker of CA Lesional Hemorrhage.

Since iron deposit in lesions is modified by ROCK inhibitor and statins in mice, the [name] group has recently applied **a novel technique for assessing iron concentration in CA lesions using**

**quantitative susceptibility mapping (QSM) on MRI.** We published validations of the technique including precise correlations of QSM with iron concentration in ferric, ferrous and ferumoxytol phantom solutions, and the exact prediction by QSM of iron content in excised CCM lesions assayed by mass spectroscopy (56). We later showed strong interobserver agreement in QSM measurements in human CAs, stability of QSM in clinically stable lesions, reproducibility of QSM across MRI instrument platforms at two hospitals, and greater lesional QSM in older patients and in cases with prior symptomatic bleeds (57).

In other pilot work we show significant correlation of mean lesional QSM in murine brains imaged *ex vivo* in the human 3T MRI magnet, with histologic iron densitometry of Perls staining of the same lesions after brain sectioning (Figure 5). This demonstrates that **differences in QSM may be used to assess the same parameter of treatment effect (lesional non-heme iron density) impacted in preclinical studies**. The observed 87.8-100% range of atorvastatin treatment effect on Perls iron stain intensity in *Ccm1* and *Ccm3* models (Figures 2-3) would correspond to an effect size of 0.043 to 0.151 ppm difference in mean lesional QSM.

[figure not shown]
*Linking QSM Change to Clinical Events in Longitudinal Follow-up of Previously Stable Human CAs.*

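### Does the ppm equivalent of the 20-point target in Section 9.3.1 (0.0068 ppm, 6-22 fold below the murine effect) undermine the effect size?

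*Combined protocol and SAP*

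**What the plan says.** Section 9.2 defines the endpoint: "The primary outcome is the mean percent change in lesional QSM per year (called the change score"). Section 9.3.1 sets the design effect on that scale: "we propose a minimum, clinically meaningful and mechanistically plausible treatment effect to be a 20% absolute difference in the mean change score". It offers three supports. The target is under half of "the mean 44% QSM increase observed with CA bleed or growth during longitudinal 1-year follow-up of previously stable lesions". It is more than three times the 5.81% threshold from the ROC analysis. And it is said to be plausible from the mouse work, because in ppm "It would be 0.0068 ppm [20% of 0.0340 ppm mean QSM change observed during follow-up of CA with SH (59)], 6-22 folds lower" than the murine treatment effect.

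The murine range comes from Section 2.2, where the effect on iron staining "would correspond to an effect size of 0.043 to 0.151 ppm difference in mean lesional QSM". The same section gives two human figures. For previously stable lesions, "CCMs with demonstrated growth or symptomatic bleeding exhibited a significant increase (+44%) in mean lesional QSM". For the pilot cohort with a bleed in the prior year, "Mean QSM in the index CA hemorrhagic lesion increased by an average of +7.93" percent per person-year epoch (16 subjects, 22 epochs).

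Section 9.3.1 sizes the trial at 20 points and shows alternatives on either side: "To detect a smaller or larger effect size, an absolute difference of 15% or 25%, 44 or 17 patients per arm would be required".

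**The concern.** The outcome is a percentage of lesion QSM, so its ppm equivalent should be a percentage of lesion QSM too. The plan instead takes 20% of something it calls a mean change. Read literally, 0.0068 ppm is the effect of shrinking the average change by one fifth, a much smaller quantity than 20 points. The claimed 6-22 fold distance below the murine effect would then come from mixing two scales.

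A second worry sits beside it. The 20 points are described as a minimum expected effect by comparison with 44%, which is the mean only of lesions that bled or grew, while the target is a difference between whole-arm means. The pilot cohort closest to the trial population averaged +7.93% per year. If placebo patients followed it, abolishing the whole rise would give 7.9 points, and a 20-point benefit would need a treated mean of about -12% per year.

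If these statements fed the sample size or the stopping rule, the trial could be aimed at an effect whose support is partly an error of scale.

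**Working it through.** **Inputs.** Target 20 points; ppm base 0.0340 (Section 9.3.1). Murine range 0.043 to 0.151 ppm; pilot mean +7.93% per epoch; stable lesions -3.2%; lesions that bled or grew +44%; ROC threshold 5.81% (Section 2.2). SD 30, within-person correlation 0, two annual scores, two-sided alpha 0.05, power 0.9 (Section 9.3.1).

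**The plan's own arithmetic reproduces.** 0.20 × 0.0340 = 0.0068. 0.043/0.0068 = 6.3 and 0.151/0.0068 = 22.2. The other two supports also check: 20/44 = 0.45, and 20/5.81 = 3.4.

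**Effect of the base.** If 0.0340 ppm is a change equal to a fraction p of lesion QSM, then lesion QSM L = 0.0340/p and the target is 0.20 × L. The value of p is not stated, so pairing it with the pilot percentage is an assumption:

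| Reading of 0.0340 ppm | L (ppm) | 0.20 × L (ppm) | Murine effect ÷ target |
|---|---|---|---|
| Change over one epoch, p = 0.0793 | 0.0340/0.0793 = 0.429 | 0.0858 | 0.50 to 1.76 |
| Change over 22/16 = 1.375 years, p = 0.1090 | 0.312 | 0.0624 | 0.69 to 2.42 |
| Change over two years, p = 0.1586 | 0.214 | 0.0429 | 1.00 to 3.52 |
| Lesion level, not a change | 0.034 | 0.0068 | 6.3 to 22.2 |

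A ratio of means only approximates mean lesion QSM. The two-year row is an outer case, since only 6 patients had two years of data. The 44% is not paired with 0.0340 ppm, because the two come from different cohorts.

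Under the first reading, 0.0068 ppm is 0.0068/0.429 = 1.6 points. As a change, it would equal 20 points only if p = 1, a mean rise of 100%, which nothing in the documents suggests.

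The last row cannot be excluded. On that reading the sentence is right and only the word *change* is wrong. The murine difference would then be 0.043/0.034 = 1.3 to 0.151/0.034 = 4.4 times the whole human lesion value, which is odd but not impossible.

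**Does the ppm figure drive anything?** The sample size uses points only. The SD of the average of two uncorrelated annual scores is 30/√2 = 21.2. With that SD, the noncentral t calculation gives exactly 25, 44 and 17 per arm for 20, 15 and 25 points. Inflation: 25/(1 - 0.375) = 40. The futility bound in Section 9.3.3 is also in points.

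**The minimum label.** SD in the pilot is about 30/1.2 = 25. Treating the 22 epochs as independent, the pilot mean is 7.93 ± 2.080 × 25/√22 = 7.93 ± 11.1, or about -3.2% to +19.0%. A 20-point benefit then puts the treated mean at 7.93 - 20 = -12.1%, with a range of -23.2% to -1.0%. At the upper end this is close to a flat course, and stable lesions themselves averaged -3.2%. The test is two-sided, and a 20-point harm (about +27.9%) is not limited by this argument at all.

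**The case for a change.** The case for acting is that the text, read as printed, is inconsistent. The endpoint definition and the ppm conversion use different bases, and under every reading in which 0.0340 ppm is a change paired with the pilot percentage, the 6-22 fold margin disappears. One of three published supports for the design effect is therefore unsafe, and correcting it would take a sentence or two. The inconsistency stands.

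The rest does not carry far. The documents contain no human lesion QSM, so a reviewer cannot supply the right figure, and one possible correction is a single word. The plausibility claim needs the target to be no larger than what was seen in mice, not many times smaller. That holds for any mean lesion QSM up to 0.151/0.20 = 0.755 ppm, which covers every row of the table.

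On the word minimum, Section 9.3.1 already says that the 44% comes from lesions with bleeding or growth, explains the sense intended, and admits that the human effect size is unknown. The +7.93% is disclosed in Section 2.2, and the same pilot supplies the SD and correlation. The 15-point row is a sensitivity figure and the 10-point bound an interim margin; neither is a rival statement of the expected effect. Preferring *target* to *minimum* is a matter of wording.

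**Conclusion.** No change is called for. As labelled, 0.0068 ppm is not the equivalent of 20 points of lesional QSM. If 0.0340 ppm and +7.93% describe the same per-epoch change, the figure is too small by a factor of about 12.6 (0.0858/0.0068), and the murine effect is 0.5 to 1.8 times the target, not 6 to 22 times. If 0.0340 ppm is a lesion level, the figure is right and the label is a slip. The documents do not settle which.

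Under either reading the consequence for the trial is nil. The effect size, the 25 per arm, the expansion to 40, the 90% power, the futility bound and the mixed model are all set in percentage points and do not use the ppm value. A reader should not rely on the 6-22 fold margin, but the weaker claim that the target is compatible with the murine data survives, provided mean lesion QSM does not exceed about 0.755 ppm. The description of 20 points as a minimum is generous beside the pilot mean, but that mean is too imprecise to contradict the target.
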